5.3.2 Exclusion Criteria

Subjects are not eligible for this study if they fulfil one or more of the following exclusion criteria:

- Treatment in the 4 weeks prior to study screening with PZQ, other anti-helminthic, anti-malarial or anti-retroviral compounds or any other medication that might affect the PK of PZQ such as certain antiepileptics (e.g., carbamazepine or phenytoin), glucocorticosteroids (e.g., dexamethasone), chloroquine, rifampicin or cimetidine (see Section 6.5.2 and Biltricide® SPC)For children being breast fed, treatment of the mothers/wet nurses with PZQ in the 3 days prior to administration of IMP
- Previous history of adverse reactions associated with PZQ treatment
- History of acute or severe chronic disease, including hepato-splenic schistosomiasis
- Marked increases of the liver transaminases (alanine aminotransferase and/or aspartate aminotransferase) above 3x ULN
- Fever defined as temperature above 38.0°C
- Debilitating illnesses such as tuberculosis, malnutrition, etc. as well as a medical history of seizures
- Mixed S. haematobium and S. mansoni infections
- Findings in the clinical examination of schistosome-infected children participating in the study as performed by the study clinician on the treatment day, that in the opinion of the

Investigator constitutes a risk or a contraindication for the participation of the subject in the study or that could interfere with the study objectives, conduct or evaluation

• Unlikelihood to comply with the protocol requirements, instructions and trial-related restrictions, e.g., uncooperative attitude, inability to return for follow-up visits, and improbability of completing the trial

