5.5.2 Withdrawal from the Trial

Subjects may withdraw from the trial at any time without giving a reason. Withdrawal of consent will be considered withdrawal from the trial.

A subject must be withdrawn if any of the following occur during the trial:

- Subject's parents or his/her legal representatives withdrew consent
- Subject lost to follow up
- Subject's participation in another clinical trial
- Any events that unacceptably endanger the safety of the subject.

Children who require malaria treatment after receiving trial treatment will not be withdrawn from the study, but because some anti-malarial agents (artemisinin derivatives) have activity against *S. mansoni*, they will be removed from the primary efficacy analysis.

If a subject withdraws from the study, no further evaluations should be performed and no attempts should be made to collect additional data, with the exception of safety data, which should still be collected, if possible.

If a subject withdraws from the study, if possible, the reason must be reported in the CRF.

If a subject is withdrawn from the study because of treatment limiting adverse event, thorough efforts should be made to clearly document the outcome.

Data obtained prior to subject's withdrawal will still be included in the efficacy and safety analysis.

Subjects withdrawn from the study will not be replaced.

If a subject does not return for a scheduled visit, all necessary measures should be taken to contact him/her. In any case, all necessary measures should be taken to document the subject's outcome, if possible.

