7.1.1 Pre-screening

Study participants will be selected from communities living in the PPD Prior to study onset, a list of all children aged 2-6 years (Part 1) and 3-24 months (Part 2) living in the selected areas will be prepared using records obtained from the latest census. At study beginning, all households in the villages will be informed about the study. Prior to performing any trial assessments that are not part of routine medical care for the subject, the Investigator or an appropriate designee (if local regulations permit) will obtain written pre-screening consent from one of the parents or a legal representative of the subject to allow the diagnosis activities and the identification of infected children, as described in Section 9.2.

Parents/legal representatives of participating subjects will be provided with plastic containers labelled with unique identification numbers (IDs) at the first day of pre-screening. They will be instructed to collect stool and urine samples of the child, each in one of the two separate containers. Stool and urine samples will be processed on the same day.

Pre-screening diagnosis of *S. mansoni* infection will be done using a single POC-CCA urine cassette test. Subjects who are positive for POC-CCA test will provide:

- One urine sample to assess *S. haematobium* co-infection using the filtration technique. One urine sample will be collected from each subject. 10 ml of urine samples will be filtered through a filter mesh which will be then examined under the microscope for *S. haematobium* egg count. *S. haematobium* positive diagnosis is defined as positive egg counts of *S. haematobium* in urine (> 1 egg/10 ml of urine) according to WHO classification: light (<50 eggs/10 ml of urine) and heavy (≥50 eggs/10 ml of urine) infections.
- Two stool samples to assess infection intensity using the Kato-Katz method. Two stool samples will be collected from each subject on different days within a maximum of 5 days, at day -28 to day -1 as baseline and 14-21 days after dosing. Infection intensity (expressed as egg count per gram of stool (epg)) will be calculated for each individual. *S. mansoni* positive diagnosis is defined as positive egg counts of *S. mansoni* in stool (>1 egg/1 occasion) according to the WHO classification: light (1-99 eggs per gram of faeces), moderate (100-399 eggs per gram of faeces) and heavy (> 400 eggs per gram of faeces) infections.

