7.1.2 Screening

Schistosome-positive subjects after assessment by the Kato Katz method together with one of their parents/legal representatives will be invited to the study hospital. The Investigator or an appropriate designee (if local regulations permit) will obtain written informed consent to allow the participation in the study and the completion of the study procedures, from one of the parents or a legal representative of the subject as described in Section 9.2.

In the hospital, the following tests/information gathering will be performed within maximum one week prior to treatment initiation:

• Clinical safety laboratory evaluations: haematology, biochemistry and urinalysis. All biological assessments will be performed in fasting condition, if possible.

- A Rapid Diagnostic Test (RDT) to detect malaria infection (one blood sample collected by finger puncture). Treatment of concomitant diseases such as malaria will be done according to the country national guidelines. Subjects who require malaria treatment before receiving the study drug will be withdrawn from the study.
- Demographic data, consisting of date of birth, gender and height
- Medical history including occurrence of seizures consisting of all previous diseases as considered relevant (relevant defined as needing medical treatment for at least 1 week) by the Investigator
- Previous medication consisting of all previous medications within the last 6 months as considered relevant by the Investigator and all regular medications within the last 6 months.
- Complete physical examination including body weight
- Vital signs in supine position including:
 - Blood pressure (systolic and diastolic) to be assessed at least 5 minutes after resting
 - Pulse rate to be assessed at least 5 minutes after resting
 - Body temperature

Subjects who fail to meet the protocol specified criteria before first dosing or withdraw their consent in the screening period before first dosing are considered screening failures. Data to be collected from these subjects are: date of informed consent, demographics, laboratory parameters (if available), AEs and reasons for non-inclusion.

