#### **Study windows:**

Visit	Activity	Trial day	Window period
Visit 1	Pre-screening	Day -28 to Day -1	-28 to -1
Visit 2	Screening / Randomisation / IMP administration / Treatment period	Day 1	1
Visit 3	End of confinement	Day 2	2
Visit 4	Follow-up	Day 3	3+1
Visit 5	Follow-up	Day 8	8
Visit 6	End of study	Day 14 to Day 21	14 to 21 +3

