## 14 Previous, Concomitant and Prohibited Medications/Procedures

**Previous medications** are medications, other than trial medications and pre-medications for trial drug, which are taken within four weeks prior to first IMP administration and if the end date of the medication < date of "study day 1".

Previous treatment will be summarized from the "Concomitant Medications" eCRF page. Anatomical Therapeutic Chemical (ATC) term 2nd level and preferred term will be tabulated as given from the WHO Drug Dictionary March 2016 version. In case multiple ATC's are assigned to a drug, all ATC-2nd level will be used for reporting.

**Concomitant treatments** are medications, other than trial medications, which are taken by subjects any time on-trial (the end date of the medication  $\geq$  date of "study day 1", or medication that is ongoing with a start date  $\geq$  date of "study day 1").

Concomitant treatment will be summarized from the "Concomitant Medications" eCRF. ATC-2nd level and preferred term will be tabulated as given from the WHO Drug Dictionary current version. In case multiple ATC's are assigned to a drug, all ATC-2nd level will be used for reporting.

**Prohibited medications** are medications, other than trial medications, listed in section 6.5.2 of the trial protocol that are taken by subjects at any time.

- Prohibited prior medications will be summarized from the "Prior Drug History" eCRF page. ATC level 2 and preferred term will be tabulated as given from the WHO Drug Dictionary version of March 2016. In case multiple ATC's are assigned to a drug, all ATC-2nd level will be used for reporting.
- Prohibited concomitant medications, which includes medications that were started prior to dosing but were not stopped prior to dosing, will be summarised and listed separately. Prohibited concomitant medications will be identified from the "Concomitant Medications" eCRF page, using Appendix B as guide. ATC level 2 and preferred term will be tabulated as given from the WHO Drug Dictionary version of March 2016. In case multiple ATC's are assigned to a drug, all ATC-2nd level will be used for reporting.

All **Concomitant Procedures**, which were undertaken any time on trial, will be summarized according to the eCRF page "Concomitant Procedure".

- Concurrent procedures will be listed by verbatim term.

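### The 4-week exclusion for praziquantel and other active drugs counts back from screening, although the baseline stool may be taken up to 28 days before that visit

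*Protocol*

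**What the plan says.** Protocol 5.3.2, repeated in the synopsis, excludes "Treatment in the 4 weeks prior to study screening with PZQ, other anti-helminthic, anti-malarial or anti-retroviral compounds". The anchor is study screening.

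The current protocol has two pre-treatment visits. At pre-screening (7.1.1) the village POC-CCA test and two Kato-Katz stools are done, the stools being collected "at day -28 to day -1 as baseline and 14-21 days after dosing". Screening (7.1.2) comes later: "Schistosome-positive subjects after assessment by the Kato Katz method together with one of their parents/legal representatives will be invited to the study hospital". There, "the following tests/information gathering will be performed within maximum one week prior to treatment initiation", and the list includes medication history. Appendix II puts screening and the eligibility check on D1 for C1-C7 and on D-7 to D1 for C8-C9. The SAP study-windows table has pre-screening as Visit 1 (Day -28 to Day -1) and "Screening / Randomisation / IMP administration / Treatment period" as Visit 2 on Day 1.

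Other text uses the word differently. Protocol 7.3.1 places the baseline stools at screening, 7.4.3 calls the POC-CCA test a screening diagnosis, and the diagnosis part of SAP 6.2 does both.

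On active co-medication, 5.5.2 takes children who need malaria treatment after dosing out of the primary efficacy analysis "because some anti-malarial agents (artemisinin derivatives) have activity against" *S. mansoni*. SAP 14 limits previous medications to those "which are taken within four weeks prior to first IMP administration".

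**The concern.** A washout protects the baseline egg count only if it is measured back from that count. Here it is measured from a later visit, so each day between the stool and screening is a day lost from the washout before the stool. A child treated shortly before pre-screening could still be passing eggs then, qualify, receive trial drug, and be egg-negative at D14-21 partly or wholly because of the earlier drug.

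Nothing later in the plan takes this child out of the primary analysis. No repeat stool is required before dosing. The mITT set needs only a baseline measurement and drops only children treated for malaria after enrolment (protocol 8.4) or after IMP (SAP 10.2). The per-protocol item on eligibility violations does not apply, because the child meets 5.3.2 as written. The protocol thus guards against active drugs taken after dosing more strictly than against those taken just before the baseline count. At stake is the absolute cure rate in each arm, which is judged against 70%, and the single-arm estimates in C8 and C9.

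**Working it through.** **1. The plan's own figure.** Protocol Table 8 gives about 85% probability of observing at least 70% cure with 50 children, 60% cure in 20 moderate/heavy and 85% in 30 light infections. The exact sum of Binomial(20, 0.60) and Binomial(30, 0.85), P(total ≥ 35), is 84.7%. The figure reproduces. The point is about timing; no sample-size figure is wrong.

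**2. Shortest interval from earlier treatment to baseline stool, on the visit definitions.** Let g be the days from stool to screening, with no Day 0 (as in SAP 11). An eligible child was treated more than 28 days before screening, so at least 29. The minimum interval to the stool is 29 − g.

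| Stool | Screening | g | Minimum interval |
|---|---|---|---|
| D-28 | D1 | 28 | 1 day |
| D-21 | D1 | 21 | 8 days |
| D-14 | D1 | 14 | 15 days |
| D-1 | D1 | 1 | 28 days |
| D-28 | D-7 | 21 | 8 days |

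The trial's earliest cure reading is 14 days after treatment. Treatment fewer than 14 days before the stool is admitted only when g is at least 16 (29 − 16 = 13). Counting the 4 weeks from the first baseline stool would give every eligible child at least 29 days.

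**3. The other reading.** If screening means the baseline stool, the washout before the stool is intact, but the criterion then ends at the stool. With a stool at D-28 and dosing on D1, 28 days are left outside it.

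**4. What covers the time between screening and dosing.** Section 7.1.2 withdraws children who need malaria treatment before study drug. For anti-helminthics there is no explicit exclusion. Section 6.5.2 requires Investigator approval for medication from screening to the end of confinement, and foresees discontinuation, after consulting the Sponsor, if a non-permitted drug becomes necessary. When screening is on D1, anti-helminthic use between stool and screening lies within the 4 weeks and is excluded.

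**5. Size.** Let p be the true cure rate and f the share of children already cured by earlier treatment though egg-positive at baseline. The expected observed rate is f + (1 − f)p, so the inflation is f(1 − p). The documents give no f; 2-5% is assumed.

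- Low end: 0.02 × (1 − 0.75) = 0.5 points.
- High end: 0.05 × (1 − 0.65) = 1.75 points.

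The probability of observing at least 35 of 50 cures, from an unstratified binomial at the inflated rate:

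| True p | f = 0 | f = 2% | f = 5% |
|---|---|---|---|
| 65% | 28.0% | 31.6% | 37.4% |
| 75% | 83.7% | 85.7% | 88.4% |

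For one such child in Part 2, the ceiling is 1/30 = 3.3 points in C8 and 1/10 = 10 points in C9. If infants were cured at 65-75% (also an assumption), the expected gain is 0.25 to 0.35 of a cure: 0.8 to 1.2 points in C8 and 2.5 to 3.5 points in C9.

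**The case against.** The strongest reply is that study screening may be meant to include pre-screening, since 7.3.1, 7.4.3 and the SAP still speak that way. That would restore the full washout before the stool. It does not rescue the text, because the same reading stops the criterion up to 28 days before dosing. Either way one interval is uncovered.

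Several other objections stand and limit the point:

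- The affected group is narrow: treated shortly before pre-screening, still POC-CCA positive and egg-positive, and with a long gap to screening. The documents give no distribution of gaps.
- Protocol 3.1 and 5.2.1 say pre-school children are not reached by control programmes, which suggests little programme praziquantel at this age.
- Egg persistence after treatment is inferred from the 14-21 day assessment window and is not stated. Section 5.5.2 says some antimalarials are active, not that they cure.
- Part 1 enrolment was planned to end in December 2017, before protocol version 3.1 (28 February 2018). New wording would in practice reach only the 40 Part 2 children.

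A reader might also infer that C8-C9 children may take antimalarials between screening and dosing. Section 7.1.2 rules that out. Or that earlier treatment would be invisible. Treatment on D-29 does fall outside the previous-medication window of SAP 14, but the same section defines prohibited drugs as taken at any time and summarises prohibited prior drugs from a separate eCRF page, and Appendix B sets no look-back. Such use could be tabulated, and a broad reading of Appendix B might remove the child from the per-protocol set. The child would remain in mITT.

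**Conclusion.** The point holds as a mis-anchored eligibility window with inconsistent use of the word screening. On the visit definitions, the shortest interval from earlier treatment to the baseline stool runs from 1 to 28 days depending on visit timing, where a rule anchored to the stool would guarantee more than 28.

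The likely effect is small: about 0.5 to 1.75 points on an arm's cure rate. This rests on an assumed f of 2-5%, true cure of 65-75%, and eggs still being shed at the baseline stool after a treatment that in fact cured.

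Two stronger conclusions are tempting and not supported. One is that each such child adds a whole cure; most would have been cured by trial drug anyway, so the expected gain is 1 − p. The other is that comparisons between arms are biased; randomisation spreads these children evenly in expectation. What is exposed is the absolute rate set against 70%, and Part 2, which has no concurrent control.

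**What to change.** Keep the 4 weeks already chosen. In 5.3.2 and the synopsis, count them back from the first baseline (pre-screening) stool, and extend the exclusion from that stool through IMP administration. Use the same term for that visit in 7.3.1, 7.4.3 and the SAP, and start the SAP 14 previous-medication look-back at the same point.

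For children already enrolled, use the 6-month medication history collected under 7.1.2 and 7.2 to flag those treated within 4 weeks before the first baseline stool. Repeat the cure-rate analysis without them as a sensitivity analysis. That history depends partly on what the Investigator thought relevant, so the flag may miss some short courses.

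The cost is a few lines of text, one extra analysis, and possibly a few more screen failures in Part 2. No new procedure or data item is needed.

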5.4 Criteria for Initiation of Trial Treatment

Not applicable

5.5 Criteria for Subject Withdrawal

5.5.1 Withdrawal from the Trial Treatment

A subject in cohort C1 who does not receive the full course of treatment (20 mg/kg t.i.d. in one day treatment) must be withdrawn from the trial. If a subject withdraws from the study treatment, no further evaluations should be performed and no attempts should be made to collect additional data, with the exception of safety data, which should still be collected, if possible. Subjects withdrawn from the trial treatment will not be replaced.

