6.5.2 Prohibited Medicines

As referred in the exclusion criteria, administration of any investigational product or use of any investigational device within four weeks prior to first administration of IMP and during the entire clinical trial is not permitted. For children being breast fed, administration of praziquantel to nursing mothers is not allowed.

Also, any medication from screening until end of confinement is not allowed without prior approval from the Investigator (except for occasional use of paracetamol or ibuprofen).

The concomitant administration of agents that induce the drug metabolising enzyme system in the liver (cytochrome P 450), such as certain antiepileptics (e.g., carbamazepine or phenytoin), glucocorticosteroids (e.g., dexamethasone) or chloroquine, may lead to reduced plasma levels of praziquantel.

The concomitant administration of rifampicin which is a strong inducer of cytochrome P 450 is contraindicated as no therapeutic effective plasma levels of praziquantel can be expected.

The concomitant administration of agents that inhibit the drug metabolising enzyme system in the liver (cytochrome P 450), e.g., cimetidine, may lead to increased plasma levels and a prolonged retention period of praziquantel.

Similarly, simultaneous consumption of grapefruit juice may lead to increased praziquantel levels.

If the administration of a non-permitted concomitant drug becomes necessary during the trial, e.g., because of AEs, the subject should be discontinued from the trial but only after consultation with the Sponsor.

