7.1.4 Follow-up visit

Follow-up visits will take place as specified in APPENDIX II.

During the 3 days following their release from the hospital, subjects will be monitored by the nurses in the health areas and/or by the community agents of the different localities for potential adverse events. If an AE is observed, the latter need to inform the medical team in charge of the study for the necessary follow up.

At day 8 (+/- 1 day), urine samples will be collected for the POC-CCA test. If an AE related to liver function occurs before hospital discharge (within 24 hours after dosing), the subject will be further monitored by the study team in the villages and an additional blood sample will be collected at Day 8 for biochemistry evaluation.

At the End of Study visit (between day 14 and 21), subjects will be asked to provide stool and urine samples for Kato-Katz method and POC-CCA test. The following tests and information gathering will be also performed:

Vital signs in supine position including:

- Blood pressure (systolic and diastolic) to be assessed at least 5 minutes after resting
- Pulse rate to be assessed at least 5 minutes after resting
- Body temperature

Complete physical examination

If a subject withdraws prematurely from the trial, every effort will be made to undertake a final examination visit as soon as possible and perform all procedures of the End of Study visit.

Any ongoing medically relevant abnormal findings at the End of Study visit, including safety laboratory tests, will be followed up until resolution or stabilization (according to Section 7.4.1.6)

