8.1 Sample Size

Part 1: this study is exploratory. There is no hypothesis testing.

The sample size is based on the minimum number of subjects to reach a meaningful precision of the primary efficacy endpoint estimate (cure rate) in each arm, taking into account the stratification factor.

Taking into account the efficacy criteria for the selection of the dose (observed cure rate >70%), through simulations, Table 8 presents the probability of observing an overall cure rate $\ge 70\%$ based on different scenarios of true cure rates based on different strata, assuming a stratification of 40% moderate/heavy infections and 60% light infections. For example, a sample size of 50 evaluable subjects provides a probability of around 85% to observe a cure rate of $\ge 70\%$ if the overall true cure rate is 75% with 40% of moderate/heavy and 60% of light infections.

Probability of observ	Assumptions of Cure Rate in Light Infections						
cure rate \geq 70%, N=50,		70%	75%	80%	85%		
	50%	15%	27%	45%	64%		
Assumptions of Cure Rate in	55%	23%	38%	57%	76%		
Moderate/Heavy Infections	60%	33%	51%	70%	85%		
inicctions	65%	45%	63%	80%	92%		

Table 8. Probability of observing an overall cure rate ≥70% based on different scenarios of true cure rates based on different strata

Assuming an approximately 17% dropout rate, 60 subjects per arm will be randomized to ensure at least 50 evaluable subjects per arm.

Part 2: 30 subjects infected with *S. mansoni* aged 13 to 24 months (C8) and 10 subjects infected with *S. mansoni* aged 3 to 12 months (C9) will be included to evaluate tolerability and efficacy.

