8.3 Endpoints

8.3.1 Primary Endpoints

Clinical cure defined as no parasite eggs in the stools 14-21 days after treatment. Egg counts will be determined by Kato-Katz method. Cure rate will be calculated for each treatment arm as the percentage of subjects becoming egg-negative 14-21 days after treatment.

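### Protocol 5.5 and 7.1.4 conflict on efficacy sampling after withdrawal, and neither secures the Day 14-21 sample that defines cure

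*Protocol*

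**What the plan says.** **Withdrawal sections.** Protocol 5.5.1 requires withdrawal from the trial in one arm-specific case: "A subject in cohort C1 who does not receive the full course of treatment". For anyone who withdraws from treatment it then limits later data to safety: "no further evaluations should be performed and no attempts should be made to collect additional data, with the exception of safety data". Section 5.5.2 carries the same limit for withdrawal from the trial: "If a subject withdraws from the study, no further evaluations should be performed". Its mandatory reasons are withdrawn consent, loss to follow-up, entry into another trial and a safety event. Section 6.5.2 adds a further route when a non-permitted drug becomes necessary: "the subject should be discontinued from the trial but only after consultation with the Sponsor".

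**Follow-up section.** For a child who withdraws prematurely, Protocol 7.1.4 says that "every effort will be made to undertake a final examination visit as soon as possible and perform all procedures" of the End of Study visit. At that visit "subjects will be asked to provide stool and urine samples for Kato-Katz method and POC-CCA test".

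**Endpoint and missing data.** Protocol 8.3.1: "Clinical cure defined as no parasite eggs in the stools 14-21 days after treatment". The SAP's visit windows (section 11) run from Day 14 to Day 21 plus 3 days, with no allowance before Day 14. SAP 10.2 keeps every randomised child with a baseline measurement in mITT, except those needing malaria treatment after dosing. Protocol 8.5.1 bases the primary analysis on mITT with imputation and uses worst case for binary endpoints. SAP 16.1.1 treats missing data as non-response, next to a sentence applying LOCF to a missing egg count.

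**The concern.** One part of the protocol tells the site to stop trying to collect efficacy data, and another tells it to try as hard as it can. A site cannot do both, and neither document ranks them. SAP 12.1 and 17.3 foresee assessments at early withdrawal but do not say how such a stool enters the cure analysis.

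The outcome involved is the primary endpoint. A withdrawn child stays in the mITT denominator, so if no usable stool exists the child counts as not cured. Worst-case imputation is a sound rule for data that cannot be obtained. Here the sample is already in the schedule and consent may still stand, so the protocol's own wording creates the gap.

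**Working it through.** **1. The plan's own figure.** Protocol 8.1 gives a probability of about 85% of observing a cure rate of at least 70% with 50 evaluable children and true cure of 60% (moderate/heavy, 20 children) and 85% (light, 30 children). The exact value is P(Bin(20, 0.60) + Bin(30, 0.85) ≥ 35) = 84.7%. It reproduces and is not in dispute. It refers to evaluable children and does not settle how withdrawn ones are handled.

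**2. The two rules applied to the same child (consent stands, child reachable).**

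| | Site follows 5.5.1/5.5.2 | Site follows 7.1.4 |
|---|---|---|
| Stool taken? | No | Yes, at a prompt final visit |
| Inside Day 14-21? | No sample | Only if withdrawal falls late; a C1 child who misses a dose is withdrawn on Day 1 |
| mITT result | Failure (Protocol 8.5.1, SAP 16.1.1) | Before Day 14: unstated, probably failure because cure is defined at 14-21 days. In window: as observed |

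Under 5.5 LOCF changes nothing for Kato-Katz cure. The only earlier count is the baseline, which is positive by the inclusion criteria, so carrying it forward also gives failure. An early egg-negative stool under 7.1.4 is the one case where LOCF and the non-responder sentence could disagree.

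**3. Who is reached.** Withdrawal from treatment concerns C1 only: SAP 17.1.2 notes that all other cohorts receive a single dose. Other cohorts are reached through 5.5.2 or 6.5.2. Withdrawn consent and loss to follow-up generally yield no sample under either text.

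**4. Size.** With n children in mITT and cure probability p for the child concerned, scoring that child as a failure instead of observing the outcome lowers the expected cure rate by p/n. The documents give no p for withdrawn children; 25% to 75% is an assumed range. The values of n are the planned cohort sizes.

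| n | p = 25% | p = 75% |
|---|---|---|
| 60 (each Part 1 arm) | 0.25/60 = 0.4 points | 0.75/60 = 1.25 points |
| 30 (C8) | 0.25/30 = 0.8 points | 0.75/30 = 2.5 points |
| 10 (C9) | 0.25/10 = 2.5 points | 0.75/10 = 7.5 points |

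These figures compare an in-window assessment with none. They size what the fix recovers per child, not the difference between following 5.5 and following 7.1.4.

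**5. Per-protocol set.** SAP 10.2 already removes children with missed doses or prohibited medicines, and those whose end-of-study stool is missing or out of window. For incomplete C1 courses and non-permitted drugs, PP is the same whichever section is followed.

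**The case against.** The strongest reply is that the conflict rarely changes a result. Section 7.1.4 wants its visit promptly, so a child withdrawn on Day 1 gives a stool far outside the window and is probably an mITT failure either way. A reader might infer that the same child is observed as cured under one section and failed under the other. The documents support that only when the final visit falls at Day 14 or later, or if an early negative stool were accepted as cure, which they do not say. This objection stands, and it is why the point is that neither section secures the sample.

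A reader might also infer a threat to the ODT dose choice. In an arm of 60 with 75% cure, P(Bin(60−k, 0.75) ≥ 42) is 85.1%, 79.8% and 73.3% for k = 0, 1 and 2 unassessed children. The arithmetic is right, but the inference assumes that withdrawn children would cure at 75% and that an in-window result was otherwise available. C1 is a reference arm and not a selection candidate, and no count of withdrawals is given for the ODT arms.

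A third tempting reading is that LOCF could turn a Day 2 or Day 8 negative POC-CCA into a cure. That is strained. SAP 16.1.1 applies LOCF to the egg count and states the non-responder rule, 16.1.2 refers back to the 16.1.1 definition, and Protocol 8.5.1 sets worst case for binary endpoints. Only a wording clarification is warranted.

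Finally, Part 1 follow-up was planned to end in December 2017, before the current protocol (28 February 2018) and SAP (31 January 2018). A change in collection can then act only on the 40 children of Part 2. This also stands.

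**Conclusion.** The contradiction is in the current text and should be removed. A child whose consent stands can be scored as an mITT failure because the protocol either forbids the sample or asks for it too early. Severity is minor: the number affected is unknown and probably small, PP is largely untouched, and the C1 route is closed if Part 1 is complete. Per child the effect is largest in C8 and C9, where a change in collection could still act; it depends on the assumed p of 25% to 75% and on the child being available at Day 14-21. The documents do not support a claim that dose selection is compromised, or that the POC-CCA cure rate is inflated.

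**What to change.** 1. **Protocol 5.5.1, 5.5.2 and 7.1.4:** reconcile them into one rule. Children who stop treatment or are withdrawn, without withdrawal of consent or loss to follow-up, are still asked for the scheduled Day 14-21 stool and urine.
2. **SAP 10.2 and 16.1.1:** use those results as observed in mITT, leave the existing malaria-treatment exclusion unchanged, and state that a sample taken before Day 14 does not count as cure.
3. **Timing:** if Part 1 follow-up is complete, apply the collection change to C8 and C9, where 5.5.2 withdrawals are the relevant route. Report the number of C1 children withdrawn under 5.5.1 beside the C1 mITT cure rate.
4. **Optional wording:** in SAP 16.1.1, 16.1.2 and 16.2.1, say that the non-responder rule governs both cure endpoints, in line with Protocol 8.5.1.

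The cost is protocol and SAP wording, plus samples already in the schedule. Dosing, withdrawal criteria and sample size do not change.
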